9.3. Variables

Baseline variables (Table 2) will be measured during the baseline period (365 days prior to the index date). Treatment patterns, adherence and persistence, and clinical variables (Table 3) will be measured during the follow-up period.

Table 2. Baseline demographic and clinical characteristic variables

Variable	Operational definition
Age	Age will be defined as of the index date and retained in the dataset as a continuous variable and a categorical variable (e.g., ≤ 59 , 60-69, 70-79, ≥ 80 years old).
Race/ethnicity	Proportion of patients that were non-Hispanic White, Black, Hispanic, other or unknown will be summarized.
Geographic regions	Proportion of patients that lived in Northeast, Midwest, South and West areas will be summarized.
Index year	A categorical variable for the index calendar year will be summarized.
Site of metastasis	Proportion of patients that had a metastatic diagnosis at the following sites: bone only, bone and node only, node

PFIZER CONFIDENTIAL

Variable	Operational definition
	only, viscera and other, will be summarized among patients with metastatic PC. All data available prior to the index date will be used.
Treatment history	
Proportion of patients who had each of the following treatments in the baseline period will be evaluated:
 
• Prostatectomy• Chronic oral corticosteroid use• Pain medication (opioids)• ADT treatment (leuprolide, degarelix, goserelin, histrelin, triptorelin)• Androgen receptor pathway inhibitor (ARPI; abiraterone, apalutamide, darolutamide, enzalutamide)• Non-steroidal anti-androgen (NSAA; bicalutamide, nilutamide, flutamide)• Chemotherapy (docetaxel, cabazitaxel, carboplatin, oxaliplatin, cisplatin, mitoxantrone)• Immunotherapy (sipuleucel-T, pembrolizumab)• Radium 223• Systemic ketoconazole• Olaparib• Rucaparib• Talazoparib• Niraparib• Lutetium Lu 177 vipivotide tetraxetan• Radiotherapy 
Treatments considered as a part of index treatment regimen will not be flagged as baseline treatments if received within 30 days prior to index date.

Time from first observed PC diagnosis date to the index date	Time from the first observed PC date in the data to the index date will be evaluated. All data available prior to the index date will be used.
NCI Charlson Comorbidity Index (CCI) score	The NCI version of the CCI score will be created during the baseline period.

Variable	Operational definition

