Comorbidities	A binary variable (yes/no) will be created for patients with a diagnosis of each of the following comorbidities during the baseline period: 
• Hypertension• Hyperlipidemia• Diabetes• Urinary tract infection• Chronic obstructive pulmonary disease• Arrhythmia• Congestive heart failure• Myocardial infarction• Stroke• Angina pectoris• Inflammatory bowel disease• Acute coronary syndrome• Sexual dysfunction• Depression• Anxiety• Hot flashes• Cognitive impairment• Major adverse cardiovascula event (defined by any evidence of cardiomyopathy, heart failure, ischemic heart disease, myocardial infarction, pulmonary embolism, or stroke)
PSA	Baseline PSA value (among available) based on the PSA value closest to the index date during the 90-day window (or 180-day, to be finalized based on the number of patients with non-missing PSA value in these time frames) on or prior to the index date will be evaluated.
Testosterone	Baseline testosterone value (among available) based on testosterone value closest to the index date during the 90-day window (or 180-day; will be consistent with the time window for baseline PSA) on or prior to the index date will be evaluated.
Metastatic vs. non-metastatic PC	A binary variable for patients with metastatic vs. non-metastatic PC will be created. Metastatic PC will be

Variable	Operational definition
	defined as having evidence of metastasis during the baseline period or within 90 days since the index date.
ADT naïve vs. ADT experienced	A binary variable for patients who were ADT naïve vs. ADT experienced will be created. ADT naïve will be defined as having no records of any systemic ADT treatment ever based on all available data prior to the index date (i.e., including baseline period data and any available data prior to the baseline period). Systemic ADT treatment includes LHRH agonists and GnRH antagonists (i.e., degarelix, relugolix, goserelin, histrelin, leuprolide, triptorelin)

Table 3. Treatment patterns, adherence, persistence, and clinical variables during the follow-up period

Variable	Operational definition

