9.5. Study size

As no priori hypotheses are specified, sample size calculations are not applicable. The number of patients eligible for the study will be determined in accordance with the sample selection conducted per the criteria described in Section 9.2.

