The same descriptive analysis described in [Section 9.7.1](#) will be conducted in Black and non-Hispanic White patients separately. If the sample sizes allow, SMD will be calculated to compare the patient baseline characteristics between Black vs. non-Hispanic White cohorts. Additionally, p-values from appropriate statistical tests (e.g., t-tests or rank-sum tests for continuous variables and chi-square tests for categorical variables) comparing Black vs. non-Hispanic White cohorts will be reported.

9.7.6. Data analysis for Objective 6: To describe and compare time to treatment changes between Black and non-Hispanic White patients with PC who initiated relugolix

The same descriptive analyses described in Section 9.7.2.3 will be conducted in Black and non-Hispanic White patients separately. Unadjusted and adjusted comparisons between the two race groups will be conducted. Cox proportional hazards (PH) regressions will be used to compare the time to treatment changes between the two race groups. Patient characteristics to be included in the adjusted models will be selected based on findings in Section 9.7.5 and clinical input.

9.7.7. Data analysis for Objective 7: To estimate and compare adherence and persistence with relugolix between Black and non-Hispanic White patients with PC who initiated relugolix

The same descriptive analyses described in Section 9.7.3 will be conducted in Black and non-Hispanic White patients separately. Unadjusted and adjusted comparisons between the two race groups will be conducted. Generalized linear models will be used to compare adherence to relugolix between the two race groups. Cox PH regressions will be used to compare persistence between the two race groups. Patient characteristics to be included in the adjusted models will be selected based on findings in Section 9.7.5 and clinical input.

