Appendix Table 2. Diagnosis codes for comorbidities

Conditions and comorbidities	ICD-10-CM
NCI comorbidity index¹	
Cerebrovascular disease	G45, G46, H34.0, I60–I69
Chronic pulmonary disease	I27.8, I27.9, J40–J47, J60– J67, J68.4, J70.1, J70.3
Congestive heart failure	I09.9, I11.0, I13.0, I13.2, I25.5, I42.0, I42.5–I42.9, I43, I50, P29.0
Dementia	F00–F03, F05.1, G30, G31.1
Diabetes with chronic complication	E10.2–E10.5, E10.7, E11.2– E11.5, E11.7, E12.2–E12.5, E12.7, E13.2– E13.5, E13.7, E14.2–E14.5, E14.7
Diabetes without chronic complication	E10.0, E10.1, E10.6, E10.8, E10.9, E11.0, E11.1, E11.6, E11.8, E11.9, E12.0, E12.1, E12.6, E12.8, E12.9, E13.0, E13.1, E13.6, E13.8, E13.9, E14.0, E14.1,

PFIZER CONFIDENTIAL

CT24-WI-GL02-RF02 5.0 Non-Interventional Study Protocol Template For Secondary Data Collection Study 01-Aug-2023
Page 37 of 41

	E14.6, E14.8, E14.9
Hemiplegia or paraplegia	G04.1, G11.4, G80.1, G80.2, G81, G82, G83.0–G83.4, G83.9
Mild liver disease	B18, K70.0– K70.3, K70.9, K71.3–K71.5, K71.7, K73, K74, K76.0, K76.2–K76.4, K76.8, K76.9, Z94.4
Moderate or severe liver disease	I85.0, I85.9, I86.4, I98.2, K70.4, K71.1, K72.1, K72.9, K76.5, K76.6, K76.7
Peripheral vascular disease	I70, I71, I73.1, I73.8, I73.9, I77.1, I79.0, I79.2, K55.1, K55.8, K55.9, Z95.8, Z95.9
Renal disease	I12.0, I13.1, N03.2–N03.7, N05.2–N05.7, N18, N19, N25.0, Z49.0– Z49.2, Z94.0, Z99.2
Individual conditions	

PFIZER CONFIDENTIAL

CT24-WI-GL02-RF02 5.0 Non-Interventional Study Protocol Template For Secondary Data Collection Study 01-Aug-2023

Page 38 of 41

Hypertension	H35.039, I10–I13, I15–I16, I67.4
Hyperlipidemia	E78.00, E78.01, E78.1, E78.2, E78.3, E78.41, E78.49, E78.5
Type II diabetes	E10.0, E10.1, E10.6, E10.8, E10.9, E11.0, E11.1, E11.6, E11.8, E11.9, E12.0, E12.1, E12.6, E12.8, E12.9, E13.0, E13.1, E13.6, E13.8, E13.9, E14.0, E14.1, E14.6, E14.8, E14.9
Urinary tract infection	
Chronic obstructive pulmonary disease	J40, J41, J42, J43, J47, J44.9
Arrhythmia	I47.0, I47.2, I49.0, I46, I49.3, I49.49, I47.9, I49.40, I49.5, I49.8, I49.9
Congestive heart failure	I09.9, I11.0, I13.0, I13.2, I25.5, I42.0, I42.5–I42.9, I43, I50, P29.0
Myocardial infarction	I21, I22, I25.2

Stroke	I60, I61, I62, I64, I65, I67, H34.1, H34.23, H34.21, H34.0
Angina pectoris	I20
Inflammatory bowel disease	K50, K51
Acute coronary syndrome	I24, I21
Sexual dysfunction	F52.21, N52
Depression	F20.4, F31.3- F31.5, F32, F33, F34.1, F41.2, F43.2
Anxiety	F06.4, F41, F43.22, F43.23, F93.0

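### The COPD flag takes only J44.9 from category J44, so a man whose sole qualifying baseline code is another J44 subcode is recorded as not having COPD

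*Combined protocol and SAP*

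**What the plan says.** Appendix Table 2 (Annex 2) defines COPD twice over in related forms. Under the individual conditions, the COPD row is "J40, J41, J42, J43, J47, J44.9". Under the NCI comorbidity index, the chronic pulmonary disease row begins "I27.8, I27.9, J40–J47" and continues with further lung codes.

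Table 2 in Section 9.3 says how a code list becomes a variable: "A binary variable (yes/no) will be created for patients with a diagnosis of each of the following comorbidities during the baseline period". Section 9.3 sets that period at the 365 days before the index date. COPD is one of the 18 comorbidities listed there.

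The flag is then used in three places. Section 9.7.1 describes it for the whole cohort and, if numbers allow, compares metastatic with non-metastatic patients by standardized mean difference. Section 9.7.5 compares it between Black and non-Hispanic White patients, with p-values. Sections 9.7.6 and 9.7.7 may adjust for it: "Patient characteristics to be included in the adjusted models will be selected based on findings in Section 9.7.5 and clinical input".

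**The concern.** J44 is the only category in the COPD row that is not taken whole. J40 to J43 and J47 enter at category level, while J44 enters through a single subcode. A row that admits five whole categories does not read as a deliberately strict definition, and neither Section 9.3, the analysis sections nor the limitations in Section 9.9 give a reason. Annex 1 lists no stand-alone documents, so the plan points to no separate code list that would fill the gap.

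What is at stake is the accuracy of one line in the baseline table. Describing baseline characteristics is the study's only primary objective, so the line should count the men it claims to count. The same line feeds the race comparison of Objective 5, and through that it could enter the choice of covariates for Objectives 6 and 7.

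**Working it through.** The plan states no figure for COPD, and Section 9.5 gives no sample size, so there is nothing to reproduce. The check is to match codes against the two rows and then apply the flag rule. A three-character entry is read as covering every subcode beneath it.

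**Step 1. Single codes against the two rows**

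| Code | Individual COPD row | NCI chronic pulmonary disease row |
|---|---|---|
| J40, J41.0, J42, J43.9, J47.9 | yes | yes |
| J44.9 | yes | yes |
| J44.0 | no | yes |
| J44.1 | no | yes |
| J45.909 | no | yes |

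**Step 2. Baseline histories under the any-listed-code rule**

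| Codes recorded in the 365 days | COPD flag as written | COPD flag with J44 whole |
|---|---|---|
| J44.0 only | no | yes |
| J44.1 only | no | yes |
| J44.0 and J44.1 | no | yes |
| J44.1 and J44.9 | yes | yes |
| J44.1 and J43.9 | yes | yes |

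Only the first three histories change. In each of them the NCI row is already met, so the Charlson component is the same before and after the change.

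**Step 3. Direction.** Leaving codes out of an any-code rule can turn a yes into a no and never the reverse. Reported prevalence can therefore only be too low, overall and within each race group. The difference between race groups could move either way, depending on which group has more of the missed men. The documents do not say.

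**Step 4. Size, on assumptions.** Let p be the true COPD prevalence in the cohort and s the share of men with COPD who have no listed code in baseline. Neither is in the documents. I take p from 15% to 25% and s from 1% to 10%.

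Reported prevalence = p × (1 − s); understatement = p × s.

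| p | s | Reported | Understatement (points) |
|---|---|---|---|
| 15% | 1% | 14.85% | 0.15 |
| 15% | 5% | 14.25% | 0.75 |
| 15% | 10% | 13.50% | 1.50 |
| 25% | 1% | 24.75% | 0.25 |
| 25% | 5% | 23.75% | 1.25 |
| 25% | 10% | 22.50% | 2.50 |

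The range is 0.15 to 2.5 percentage points.

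**The case against.** The strongest reply is that the two rows define different variables. The NCI row is a Charlson component adapted from a published algorithm, as the table's footnote says, and is broader on purpose. It also takes in J45 and J46, J60 to J67 and two I27 codes. Some codes are meant to count in the index and not as COPD. That stands: a reader might infer that the table contradicts itself, and it does not. The case rests on the COPD row alone, where one category is cut to a subcode beside five whole ones. The NCI row shows only that the omitted codes are counted elsewhere in the same analysis.

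A reader might also infer that every man with a J44.0 or J44.1 code is lost. The flag rule does not support this. One listed code at any time in 365 days is enough, so a man who also has J44.9, or any of the other listed categories, is counted.

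A third tempting step is to say that the omitted codes mark sicker men and so bias the flag by severity. The documents do not describe what these subcodes mean. The inference is also uncertain on its own terms, because men with more contacts in the year have more chances to receive a listed code as well.

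Finally, the effect may be very small. This is one of 18 comorbidities in a study whose Section 9.5 says "As no priori hypotheses are specified, sample size calculations are not applicable". That bears on priority and leaves the error in the flag as it is.

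**Conclusion.** The point holds in a limited form. As written, the COPD row gives the wrong flag to a man whose only qualifying baseline code is a J44 subcode other than J44.9, and the plan offers no reason for the restriction. The consequence is a one-way understatement of COPD in the Objective 1 baseline table and in the Objective 5 race groups. It carries into the adjusted models of Objectives 6 and 7 only if COPD is selected as a covariate.

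The number of men affected cannot be worked out from the documents. The 0.15 to 2.5 points rest wholly on the assumed prevalence and assumed share missed, and should be read as a range of possibilities and not as an estimate. The NCI Charlson score, cohort selection, and the treatment-pattern, adherence, persistence, PSA and testosterone definitions do not use this row and are unaffected. This is a minor correction, worth making because it is easy and sits in a primary-objective table.

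**What to change.** In the individual COPD row of Appendix Table 2, replace J44.9 with J44 and state that all subcodes are included. If the restriction to J44.9 is intended, the alternative is to give the reason beside the row.

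The cost is one entry in a code list and a rerun of the COPD flag. No new data are needed and the cohort does not change. Running the flag both ways once would also show how many men move from no to yes, which would replace the assumed range above with a count.

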9.7. Data analysis

9.7.1. Data analysis for Objective 1: To describe demographics and clinical characteristics of patients with PC who initiated relugolix

Descriptive analysis will be conducted for baseline demographics and clinical characteristics. Means, standard deviations, medians, and interquartile range will be estimated for continuous variables. Counts and percentages will be estimated for categorical variables. If the sample sizes allow, standardized mean difference (SMD) will be calculated to compare the patient baseline characteristics between metastatic vs. non-metastatic PC cohorts. For each variable, the SMD will be calculated as the difference in mean between two cohorts divided by the standard

deviation of the two cohorts pooled together. The absolute value of a SMD $> 10\%$ will be considered as an indicator for significant imbalance.

9.7.2. Data analysis for Objective 2: To assess treatment patterns among patients with PC who initiated relugolix

[figure not shown]

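### The baseline Stroke code row includes codes that are not stroke and omits I63, so the flag is misclassified in both directions

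*Combined protocol and SAP*

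**What the plan says.** Section 9.3, Table 2 lists Stroke among 18 baseline comorbidities and treats them all alike: "A binary variable (yes/no) will be created for patients with a diagnosis of each of the following comorbidities during the baseline period". No second code, care setting or other confirmation is asked for, so one qualifying record in the 365 days before index sets the flag.

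The codes are in Annex 2, Appendix Table 2, under an ICD-10-CM column. The Stroke row is "I60, I61, I62, I64, I65, I67, H34.1, H34.23, H34.21, H34.0". The Cerebrovascular disease row, in the part of the table that feeds the NCI comorbidity index, is "G45, G46, H34.0, I60–I69".

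Table 2 also defines a major adverse cardiovascular event flag, "defined by any evidence of cardiomyopathy, heart failure, ischemic heart disease, myocardial infarction, pulmonary embolism, or stroke". This composite has no code row. Three of its components (cardiomyopathy, ischemic heart disease, pulmonary embolism) have no row of that name either, and nothing says which codes serve its stroke component.

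The flags are used in three places:
- Section 9.7.1, the primary objective, reports them as counts and percentages and, sample size permitting, compares metastatic with non-metastatic men by standardized mean difference (SMD) against a 10% threshold.
- Section 9.7.5 repeats this for Black and non-Hispanic White men and adds p-values.
- Sections 9.7.6 and 9.7.7 choose adjustment covariates from the 9.7.5 findings together with clinical input.

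**The concern.** A row labelled Stroke should pick out men with a stroke diagnosis. This one errs both ways. It flags men whose only code is for narrowed neck arteries, for a residual class of cerebrovascular disease, or for a transient retinal occlusion. It also passes over men whose only code is for cerebral infarction.

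These are faults in the code list, not in the records. The coding limitation in Section 9.9 concerns diagnoses entered wrongly or as rule-outs. Here a correctly coded carotid stenosis becomes a stroke, and a correctly coded infarction does not.

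What is at stake is one line of the primary-objective table, the same line in the metastatic and race comparisons, and possibly the cardiovascular composite. The rationale in Section 7 discusses cardiovascular risk under androgen deprivation, so readers are likely to look at these lines.

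**Working it through.** The plan gives no stroke prevalence, sample size or error rate, so there is no figure to reproduce. The check is a comparison of code sets followed by an illustrative count. Code meanings are the category headings of ICD-10-CM, the system named in the table; the protocol does not print them.

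**1. What the row contains**

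| Codes in the Stroke row | Heading | Stroke? |
|---|---|---|
| I60, I61, I62, I64 | the row's remaining I-codes | not disputed here |
| I65 | precerebral occlusion or stenosis not resulting in infarction | no |
| I67 (whole category) | other cerebrovascular diseases | no |
| H34.0 | transient retinal artery occlusion | no |
| H34.1, H34.21, H34.23 | other retinal artery occlusion codes | depends on the intended definition |

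**2. What the row omits.** The I-code categories in I60–I69 that are absent from the Stroke row are I63, I66, I68 and I69. The point rests on I63 (cerebral infarction) alone.

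**3. Net error.** Leave the three debatable retinal codes aside. Let:
- t = men with a stroke code that the row retains;
- m = men with I63 and no code in the row;
- x = men with I63 who are flagged only because they also carry I65, I67 or H34.0;
- f = men with I65, I67 or H34.0 and no stroke code at all.

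Men with a stroke code: t + m + x. Men flagged as written: t + f + x. Net error as written = (t + f + x) − (t + m + x) = f − m.

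If codes are only deleted, men flagged = t, and the net error is −(m + x), never positive.

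If codes are deleted and I63 is added, men flagged = t + m + x, and the net error is 0.

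**4. Illustration per 1,000 men.** All inputs are assumed, none is from the documents: t = 10, x = 0, m from 10 to 40, f from 0 to 60.

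| m | f | True (t + m) | As written (t + f) | Net (f − m) | Deletion only (−m) |
|---|---|---|---|---|---|
| 40 | 0 | 50 | 10 | −40 | −40 |
| 20 | 20 | 30 | 30 | 0 | −20 |
| 10 | 60 | 20 | 70 | +50 | −10 |

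The middle line shows why a small net error would not clear the row. The percentage is right, yet 20 of the 30 flagged men have no stroke code and 20 of the 30 men with one are missed.

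**5. Composite.** If the composite uses this row, a man in f changes it only when he has none of the other five components, and so does a man in m. Its net error is the same difference restricted to those men. The documents give no count of them.

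**The case against.** Several counter-arguments have force.

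- **Direction.** A reader might infer from I65 and I67 that stroke will be over-reported. The documents do not support this. The missing I63 pulls the count down, and nothing in the plan says which effect is larger. For the same reason, no share of falsely flagged men can be stated without prevalences that the plan does not give.
- **Overlap with Hypertension.** That row, "H35.039, I10–I13, I15–I16, I67.4", contains I67.4, which also falls under I67 in the Stroke row. A reader might call this a contradiction. It is not. The flags are separate and the table shares codes elsewhere: I21 is in both Myocardial infarction and Acute coronary syndrome, and I11.0 is in Congestive heart failure while lying inside the I10–I13 range for Hypertension.
- **Narrower row.** No rule in the plan makes an individual condition narrower than its index counterpart; Congestive heart failure has the same codes in both places. The case therefore rests on what the codes mean and on the label Stroke.
- **Composite.** The plan does not say that the composite draws on this row. It is the only stroke code list in the protocol, and Annex 1 lists no stand-alone documents, so its use is the natural reading but still an inference.
- **Retinal codes.** The sponsor may count retinal infarction as stroke. That is a choice of definition, provided that it is stated.
- **Importance.** Stroke is one of 18 comorbidities, the analysis is descriptive, and Section 9.5 says "As no priori hypotheses are specified, sample size calculations are not applicable". Covariates are not yet chosen, so an effect on the adjusted models is possible, not established.

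These points limit direction, size and reach. They do not remove the error: adding I63 would not unflag a man with only carotid stenosis, and deleting I65 and I67 would not capture a man with only I63.

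**Conclusion.** Wrong as written. The Stroke row admits I65, all of I67 and H34.0, which are not stroke, and omits I63, which is. The baseline stroke flag is therefore misclassified in both directions in the primary-objective table and in the metastatic and race comparisons.

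The sign and size of the net error cannot be determined from the documents. The span of −40 to +50 per 1,000 shows only that either sign is possible under the assumed inputs; it is not an estimate. The composite is affected to the extent that it uses this row and the man has no other component.

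The conclusion rests on the standard ICD-10-CM headings and on the row being applied as printed. It does not touch cohort selection, adherence, persistence or the response outcomes.

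**What to change.** Make these changes together in Appendix Table 2, because deletion alone would leave a pure under-count:

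1. Remove I65, I67 and H34.0 from the Stroke row.
2. Add I63.
3. Keep H34.1, H34.21 and H34.23 only if retinal infarction is meant to count, and label the row accordingly.
4. State the code list for the major adverse cardiovascular event composite, and build its stroke component from the corrected row.
5. If the wider concept is of interest, report it as a separate line called Cerebrovascular disease.

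The cost is an edit to one code row and a short code list for the composite. It needs no new data and does not change the cohort.

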Cognitive impairment	G30, G31.0, F01, F05, R41.0, R41.82, F10.1, F10.2, G31.2, G31.83, F02, F03, G31.1, G31.84, F06.7, R41.3, R41.81, R41.840
Hot flashes	R23.2
Primary cancers	C00-C21, C22.1-C22.7, C23-C76, C80.1, C80.2, C81-C96, C7A

Abbreviations: ICD-9-CM: International Classification of Diseases, 9th Revision, Clinical Modification; ICD-10-CM: International Classification of Diseases, 10th Revision, Clinical Modification; NCI: National Cancer Institute

[1] Source: Quan, Hude, et al. Coding algorithms for defining comorbidities in ICD-9-CM and ICD-10 administrative data. Medical care (2005): 1130-1139. Adapted using codes found in NCI Comorbidity Index Overview: <https://healthcaredelivery.cancer.gov/seermedicare/considerations/comorbidity.html>

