Appendix Table 3. Codes for corticosteroids and pain medications

Treatment	GPI	HCPCS
Corticosteroids	22, 8910, 8915	C9256, J0702, J0704, J1020, J1030, J1040, J1094, J1100, J1700, J1710, J1720, J2650, J2920, J2930, J3300, J3301, J3302, J3303, J7312, J7506, J7509, J7510, J7512, J7624, J7626, J7627, J7633, J7634, J7637, J7638, J7683, J7684, J8540
Pain medications (analgesics)		
Opioids	65	

Abbreviations: GPI: Generic Product Identifier; HCPCS: Healthcare Common Procedure Coding System

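### The cognitive impairment flag counts men with only an alcohol abuse or dependence diagnosis; separately, the chronic oral corticosteroid variable does not match its code list

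*Combined protocol and SAP*

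**What the plan says.** **Cognitive impairment.** Table 2 in Section 9.3 lists "Cognitive impairment" among the baseline comorbidities, under the rule "A binary variable (yes/no) will be created for patients with a diagnosis of each of the following comorbidities during the baseline period". The baseline period is the 365 days before the index date. The code list in Annex 2, Appendix Table 2, has 18 entries, among them "G30, G31.0, F01, F05, R41.0, R41.82, F10.1, F10.2, G31.2, G31.83". No fifth or sixth character limits F10.1 or F10.2, and no second diagnosis is required. The same appendix table has another list in this area, the Dementia row of the NCI comorbidity index, which reads "F00–F03, F05.1, G30, G31.1" and has no F10 code.

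**Corticosteroids.** The treatment history row of Table 2 names "Chronic oral corticosteroid use" under the rule "Proportion of patients who had each of the following treatments in the baseline period will be evaluated". The only corticosteroid code list is in Appendix Table 3, titled "Codes for corticosteroids and pain medications". Its row is labelled simply as corticosteroids. It gives GPI prefixes 22, 8910 and 8915 and a set of HCPCS codes that includes "J2920, J2930, J3300, J3301, J3302, J3303, J7312, J7506, J7509, J7510, J7512, J7624, J7626, J7627". No route filter, days-supply rule or definition of chronic use appears anywhere.

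**Use of the variables.** Baseline characteristics are the whole endpoint of the primary objective (Table 1, Section 9.7.1). They are compared between Black and non-Hispanic White patients in Section 9.7.5. Those findings, with clinical input, inform the covariates for the adjusted models in Sections 9.7.6 and 9.7.7.

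**The concern.** A baseline table is only as good as the match between each row's label and the codes behind it. In ICD-10-CM, F10.1 and F10.2 are substance-use categories. Some of their subcodes describe impaired cognition, but most describe alcohol use with no statement about cognition. Taking the categories whole puts cognitively normal men in the impaired row.

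Two results are exposed. The report could misstate how often relugolix is started in men with impaired cognition, which is part of the primary result. In the race comparison, a difference in alcohol coding could be read as a difference in cognition, and the variable could enter an adjusted model under the wrong name.

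The corticosteroid variable has a milder form of the same problem. Its name promises two restrictions, chronic and oral, that neither the rule nor the code list supplies.

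**Working it through.** The plan states no prevalence, sample size or expected rate for either variable, so there is no figure to reproduce. Code meanings below are those of the standard ICD-10-CM and HCPCS sets that the plan uses; the documents do not print them.

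**1. Who is flagged as cognitively impaired.** Two of the 18 entries are whole alcohol-use categories. With the Table 2 rule, one baseline diagnosis in F10.1 or F10.2 is enough. No other sentence in the documents removes such a man.

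**2. Illustrative size.** Let p be true cognitive impairment and q the proportion with an alcohol-use code of no cognitive meaning, independent of p. Both are assumptions: p = 5-10%, q = 5-15%. Then

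flagged prevalence = p + q(1 − p), and alcohol-only share of flagged men = q(1 − p) / flagged prevalence.

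| p | q | Flagged prevalence | Flagged / true | Alcohol-only share |
|---|---|---|---|---|
| 5% | 5% | 5 + 4.75 = 9.75% | 1.95 | 4.75/9.75 = 49% |
| 5% | 15% | 5 + 14.25 = 19.25% | 3.85 | 14.25/19.25 = 74% |
| 10% | 5% | 10 + 4.5 = 14.5% | 1.45 | 4.5/14.5 = 31% |
| 10% | 15% | 10 + 13.5 = 23.5% | 2.35 | 13.5/23.5 = 57% |

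So prevalence runs from 9.75% to 23.5%, and the ratio to the true value from 1.45 to 3.85.

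**3. Race comparison.** Suppose both groups have p = 5%, so there is no true difference. Take the SMD as the difference in proportions over the root of the mean of the two variances.

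- q = 5% vs 10%: flagged 9.75% vs 14.5%. SD = √[(0.0975×0.9025 + 0.145×0.855)/2] = 0.3256. SMD = 0.0475/0.3256 = 0.146.
- q = 5% vs 8%: flagged 9.75% vs 12.6%. SD = √[(0.0975×0.9025 + 0.126×0.874)/2] = 0.3147. SMD = 0.0285/0.3147 = 0.091.

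Section 9.7.1 treats an absolute SMD above 10% as imbalance. Section 9.7.5 does not restate the threshold; I assume that it carries over. The first case exceeds it and the second does not.

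**4. Corticosteroid list.** Appendix Table 3 has 33 HCPCS codes. By standard meaning 5 are oral (J7506, J7509, J7510, J7512, J8540), 17 injected, 9 inhaled and 2 intravitreal implants (C9256, J7312): 17 + 9 + 2 = 28 non-oral, and 28 + 5 = 33. The GPI entries are class prefixes with no route limit. If the list is applied as printed under the Table 2 rule, a single injection or one inhaled product sets the flag.

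**The case against.** **Corticosteroids.** The strongest reply is that Appendix Table 3 is a general list and that chronic and oral are qualifiers in Table 2, to be applied in programming. A code list cannot by itself express duration. This stands in part. A reader might infer that the corticosteroid prevalence is inflated, but no passage says that every listed code sets the chronic oral flag. What is established is that the name and the list do not match and that both qualifiers are undefined. Nor does 28 of 33 measure the effect: a share of code strings is not a share of patients, and oral products can also enter through the GPI column.

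**Cognition: size.** The rates in the working are assumed. A reader might infer that the flag mostly measures alcohol use, or that it doubles the prevalence. Neither is supported: at the four combinations tabulated, the alcohol-only share runs from 31% to 74% and the ratio from 1.45 to 3.85. The spurious race difference is also conditional, as the 5% vs 8% case shows.

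**Cognition: intent.** Some F10.2 subcodes do describe amnestic disorder or dementia. The row is also wider than dementia, since F05, R41.0 and R41.82 cover delirium, disorientation and altered mental status. Alcohol-related delirium therefore fits its scope, and a fix that kept only F10.26 and F10.27 would cut too far. This shapes the remedy but does not justify the whole categories.

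**Reach.** Neither variable enters an eligibility criterion or an outcome definition, and covariate selection concerns exploratory objectives and also uses clinical input. That is correct and limits the consequence.

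**Conclusion.** The cognitive impairment point holds. As written, the row and the flag rule count men with only an alcohol abuse or dependence diagnosis as cognitively impaired, and nothing in the documents prevents it. The direction is certain if any included man has such a record and no cognitive one: the row is overstated. The size cannot be obtained from the documents; the range in the working rests wholly on the assumed rates and on independence. The effect is confined to one descriptor under the primary objective, its race comparison under Objective 5, and its possible use as a covariate under Objectives 6 and 7.

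The corticosteroid point holds only as a mismatch between name and list, with two undefined terms. Inflation would follow if the list were applied as printed, but the documents do not say that it will be. They also give no basis for removing GPI 8910 or 8915 in particular, or for any specific days-supply threshold.

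Both should be settled before the baseline tables are produced, so that the definitions are not chosen after the results are seen.

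**What to change.** **Cognitive impairment row, Appendix Table 2.** Replace F10.1 and F10.2 with only those subcodes that denote impaired cognition: F10.26 (persisting amnestic disorder), F10.27 (persisting dementia) and, because the row already includes delirium, the alcohol-related delirium subcodes, such as F10.121, F10.221 and F10.231. Check the final list against the ICD-10-CM editions in force over the baseline periods. If alcohol use is of interest, report it as its own flag.

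**Corticosteroid variable, Table 2 and Appendix Table 3.** Either limit it to oral-route products, filtering both the GPI and the HCPCS entries by route, and state the days-supply rule that makes use chronic; or keep the list and rename the variable as any corticosteroid use.

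**Cost.** These are edits to text and code lists and need no new data. The reported prevalence of cognitive impairment will be lower, as will that of corticosteroid use if the list would otherwise have been applied as printed. A separate alcohol flag adds one row.
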